Our central hypothesis is that an enhanced SRH curriculum (including a comprehensive module on HIVST, contraceptives and PrEP) and the additional offering of HIVST and contraceptive services at the event along with ongoing engagement the SKILLZ-Club program (Enhanced Arm) , will increase HIV testing and contraceptive uptake compared to the standard SKILLZ curriculum & standard event (SOC Arm). Furthermore, supporting subsequent ongoing education as well as linkage to services through SKILLZ school clubs in the enhanced arm will improve ongoing uptake of services and retention and will allow us the opportunity to measure the effect of the intervention longitudinally. We further hypothesize that our intervention will positively and directly affect a number of mediating factors: attendance to soccer events where community-based SRH services are offered, SRH knowledge, empowerment, self-confidence, and perceptions of gender balance, and (reduced) stigma. For girls found to be HIV-positive, we further expect the follow-on SKILLZ intervention (SKILLZ-Plus) aimed at linkage to HIV care and treatment, will reduce HIV-related stigma, increase disclosure to family and partners, increase feelings of social support, empowerment, self-efficacy, and ultimately adherence to ARVs, viral load suppression (VLS) and retention in HIV care and treatment.

The SKILLZ program trains young adult mentors (“Coaches”) as community change agents that deliver age-appropriate, gender-transformative curricula through a pedagogical approach that combines soccer metaphors and activities with accurate health information. The aim is to build the health and social assets of adolescents, facilitate access to health and social services, and support adherence to medical treatment and positive protective behaviors.

c. Evidence supporting the justification

[figure not shown]

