2. **Enhanced SKILLZ-Girl** is based on the curriculum described however we have modified the regular SKILLZ-Girl curriculum to include a focused module on HIVST, PrEP and contraception. In our study we will be comparing the 'regular' SKILLZ girl curriculum with this 'enhanced curriculum. The enhanced curriculum is based on the same premises and methodology as SKILLZ-girl.

Both SKILLZ-Girl and SKILLZ-Girl enhanced focus on building adolescent girls' health and social assets, culminating in a soccer tournament to address detrimental social norms and attitudes towards girls and disrupt traditional service delivery models with several salient features:

- *Building individual self-efficacy, empowerment and future orientation through the SKILLZ-Girl and enhanced curriculum:* A series of 10-12 x 1.5-hour sessions will be delivered by coaches (1 coach for every 25 girls) over approximately 12 weeks at school during normal school hours. The curriculum validates experiences of puberty and sexuality while building life skills and other critical assets that are broadly applicable to many spheres of girls' lives. It provides a link to a range of behavioral outcomes including stigma prevention, SRH and contraception, all designed to create an integrated health package for young women. The curriculum culminates in a soccer event where participants will be offered an opportunity to either test for HIV at the event or (depending on intervention arm) take home a HIVST kit, take up a contraceptive method or be assessed for uptake of PREP. The Permanent Secretary for MOH has provided support to conduct this assessment particularly in improving access to PREP for at-risk adolescent girls (*see Appendix C*).
3. Following the community soccer event, in the enhanced arm, all girls (regardless of HIV or testing status) will be invited to participate in **SKILLZ-Club**. These school-based clubs are run in the afternoons during extra-curricular hours and provides students with an opportunity to continue to engage in a deeper discussion about SRH, empowerment, HIV prevention and HIV testing. SKILLZ-Club also focuses on contraception initiation and continuation as a tool for future planning, self-care and empowerment. It also includes participation in a community change project that continues to build self-efficacy and agency. The club is an

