GRS has shown that soccer-based interventions combined with strong school and community partnerships and referral networks can change behaviors and make a significant impact on the health of young people.⁵³ In 2009 in South Africa, GRS piloted the SKILLZ-Girl program which addresses the unique needs of young women and adolescent girls. This program was then scaled in South Africa and expanded further into 13 countries in SSA. A recent evaluation of the SKILLZ-Girl program showed that participants significantly improved their knowledge and attitudes surrounding HIV risk for young women, negotiation skills, and sense of self-efficacy. In fact, 68.5% of girls that participated in the SKILLZ-Girl program underwent testing for HIV at the conclusion of the school-based curriculum.⁵⁴ Although SKILLZ-Girl has now served over 26,000 girls in 14 countries, it has never been rigorously evaluated for cost effectiveness and effectiveness.

6. Research questions

Our mixed-methods evaluation aims to assess the effect of the enhanced SKILLZ- girl on HIV testing and SRH related prevention services uptake (Aim 1), the effect of SKILLZ-Plus on HIV retention to care and VLS amongst HIV-infected girls (Aim 2) and identify mediating pathways and moderating factors leading to observed effects (Aim 3). Aim 3 will also assess the cost-effectiveness of the SKILLZ Package.

Our research questions are thus:

- a. What is the impact of enhanced SKILLZ-Girl vs regular SKILL-girl curriculum on HIV testing uptake among adolescent girls (aged 16 and over) over a 24-month period?
- b. What is the impact of enhanced SKILLZ-Club on HIV testing uptake among adolescent girls (aged 16 and over) over a 24-month period?
- c. Among HIV-positive adolescent girls, what is the impact of the SKILLZ-Plus intervention on:
 - a. retention in care and treatment at 6, 12, and 24 months
 - b. viral load suppression at 12 months?

- d. What specific barriers to access to services do the SKILLZ interventions (SKILLZ Girl, enhanced SKILLZ-girl, SKILLZ-Club & Plus) overcome?
- e. What are the mediators of the observed effects?
- f. What are the moderators of the observed effects?
- g. To what degree was the intervention implemented per protocol (fidelity)?
- h. What is the short- and long-term cost-effectiveness of the SKILLZ Package intervention?

7. Research aim(s)/General Objective and Specific Objectives

Aim 1: Assess the impact of SKILLZ over two years on:

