- (i) (a) **HIV testing** and (b) SRH-related prevention services uptake among adolescent girls aged 16-19 in up to 9 intervention schools (with enhanced HIVST, PrEP, and contraceptive method offerings) compared to up to 9 control schools using a quasi-experimental difference-in-difference approach; and
- (ii) **linkage to care and treatment, and viral load suppression and retention at 6, 12, and 24 months** through a cohort model using pre-existing SmartCare data on HIV+ individuals in care to match to adolescent girls aged 16 and over from the same district (Lusaka) who are identified to be HIV+ at any time during SKILLZ Girl or SKILLZ Club participation and enrolled in SKILLZ-Plus.

This will be achieved by i) using a quasi-experimental difference-in-difference approach that compares girls aged 16 and over in 9 SKILLZ control schools compared to 9 schools where enhanced SKILLZ will be delivered with the enhanced HIVST and a variety of contraceptive method offerings; and ii) through a cohort model using pre-existing SmartCare data on HIV+ individuals in care to match to adolescent girls aged 16 and over from the same district (Lusaka) who are identified to be HIV+ at any time during SKILLZ-Girl or SKILLZ-Club participation.

Aim 2: Examine how the intervention works including lessons learned for future implementation by

- (i) conducting a process evaluation to identify mediators, predictors, and barriers to uptake of the SKILLZ-Girl, Club, and Plus curricula both quantitatively through mediation and moderation analyses and qualitatively through a sequential explanatory approach using focus groups discussions, interviews and observation with coaches and girls; and by
- (ii) monitoring fidelity

Aim 3: Estimate the short- and long-term cost-effectiveness and return on investment of the SKILLZ Girl, Club, and Plus curricula for improving health outcomes for adolescent girls.

8. Methodology

a. Study design

We will conduct a mixed-methods evaluation of the SKILLZ intervention using the following approaches:

A **quasi-experimental cohort** of school-aged 16-year old and over females to be followed for a two-year period will be evaluated with a difference-in-difference (DID) approach to estimate HIV testing uptake and sexual/reproductive health services use. Primary and secondary outcomes will be measured at several

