Survey post-SKILLZ-Girl event, 3-, 12-, and 24 months: All girls (regardless of HIV status) will respond to a REDCap survey to collect information on sexual behavior, HIV knowledge, maternal education, sexual/reproductive health uptake and retention. Post-SKILLZ-Girl survey data will be used to assess the effect of SKILLS Girl and SKILLZ-Club on the outcomes of interest. In schools selected to offer SKILLZ-Club, surveys will be conducted during club attendance approximately 3 months after the SKILLZ-Girl community soccer event; coaches will help them navigate the survey. If a participant has opted to not attend the clubs or has since left or changed schools, the coaches and study staff will attempt to trace participants in the community in order to complete the follow-up survey.

In the schools selected not to offer SKILLZ-Club, GRS will arrange for a 2-hour meeting session with all participants still enrolled at that school, where all participants will complete the surveys. If a participant opts to not attend the meeting or has since left or changed schools, the coaches and study staff will attempt to trace participants in the community in order to complete the follow-up survey.

The survey will record any changes to their home environment from baseline, again ask about self-reported sexual and risk behaviors and HIV knowledge (i.e., post-test for HIV education curriculum), and further quantitatively measure potential mediating pathways. Based on validated scales, the survey will include modules to assess stigma;⁵⁷ empowerment;⁵⁸ and self-efficacy⁵⁹ in general and specific to SRH/HIV;⁶⁰ disclosure, extent of social support from different sources (e.g., family, peers, teachers), and trust in health providers.⁶¹ Individual lost to follow-up (LTFU) will be traced following standard procedures. Active follow up and tracing of late or lost patients enrolled into HIV care or receiving ART is part of the National treatment program. We will partner with pre-existing CIDRZ community volunteers responsible for follow up to ensure that efforts are synchronized, and that data are shared and entered into SmartCare. CIDRZ already has an international reputation leading effort to track those who are lost to ensure participants return for visits and viral load testing as per national guidelines.⁹⁸

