Quantitative analysis: Surveys conducted at baseline will be used to identify differential effects among girls who do and do not take up services according to baseline moderating variables as specified in **Figure 1** and as assessed by previous sexual behavior, HIV testing/status, knowledge, maternal education by interacting the main exposure by these indicators. Statistical mediation will be assessed using the causal inference-based approach of Valeri et al., which yields optimal estimates of indirect effects in the presence of binary outcomes and moderator-mediator interactions,⁶⁴ and robust standard errors to address clustering of individuals within facilities, and account for multiple causally depending mediators.⁶⁵ Significant indirect and total effects of integration markers on outcomes accompanied by non-significant direct effects will signify mediation. The interplay between exposure, effect modifiers, moderators and outcomes in the causal chain is represented in **Figure 1**. For analyses, we will use mixed effect structural equation models in STATA and MPLUS with bootstrapped standard errors to test the contribution of indirect effects.

Qualitative analysis: All interviews will be voice-recorded, transcribed and coded using a thematic analysis process⁶⁶ (e.g. in NVIVO or Atlas.ti). Analysis will begin with familiarization of the data that will involve

reading and re-reading of the transcripts to understand the data. Notes will be taken down at the point of familiarization to guide the development of the codebook. Codes will be extracted both inductively (bottom-up) and deductively (top-down). Inductively, open coding will be conducted to identify interesting and meaningful text in each line of the transcripts. Each piece of text will be grouped under a specific code that describes the meaning of the text. Once all the text has been coded, the researchers will then identify themes that tell something significant about the research questions and group a set of codes under each related theme. The themes will then be reviewed by reading each code and its associated text and re-arranged or removed in order to refine the themes and their meaning. Secondary coding will be applied to uncover the latent meaning of each of the themes. Themes will then be re-coded to uncover the latent meaning of the themes and refine their definitions.

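### The only printed rule for concluding mediation requires a non-significant direct effect, so an undetected direct effect counts as none and a real partial mediator can go unrecognised

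*Combined protocol and SAP*

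**What the plan says.** Section 8f, under the quantitative part of the process evaluation, plans a causal-inference mediation analysis for binary outcomes that will "account for multiple causally depending mediators" and use "robust standard errors to address clustering of individuals within facilities". Its decision rule is one sentence: "Significant indirect and total effects of integration markers on outcomes accompanied by non-significant direct effects will signify mediation". The same paragraph plans structural equation models with bootstrapped standard errors to test indirect effects, but does not say what conclusion follows from those tests.

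The analysis serves Aim 2 in section 7 ("conducting a process evaluation to identify mediators, predictors, and barriers to uptake of the SKILLZ-Girl, Club, and Plus curricula") and question e in section 6 ("What are the mediators of the observed effects"). The central hypothesis in section 3b is that the intervention will "positively and directly affect a number of mediating factors: attendance to soccer events where community-based SRH services are offered, SRH knowledge, empowerment, self-confidence", along with gender perceptions and reduced stigma. Section 8d says the follow-up surveys will "further quantitatively measure potential mediating pathways". No other section gives a criterion for concluding mediation.

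**The concern.** A non-significant direct effect is not evidence that there is none. It may only mean that the study was too imprecise to detect one. The printed rule has no margin or interval to tell the two apart, so low power for the direct effect makes the rule easier to satisfy.

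The rule also fails in the other direction. If a mediator carries a substantial part of the effect and the remaining direct effect is detected, the criterion cannot be met, however large and precise the indirect effect. Even if the sentence is read as a sufficient pattern and not a necessary one, the plan does not say what to conclude in that case. The call would be made after the data are seen.

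At stake is the answer to question e and Aim 2: which pathways carry the observed effects. The same mediator could be reported as mediating or not according to whether a different quantity, the direct effect, happens to reach significance.

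**Working it through.** **1. The rule by cases** (total effect significant throughout)

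| Indirect | Direct | Conclusion under section 8f |
|---|---|---|
| significant | not significant | mediation |
| significant | significant | none stated |
| not significant | either | criterion not met |

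The second row is what a well-measured partial mediator produces.

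**2. Is partial mediation plausible?** At the soccer event (section 4), "participants will be offered an opportunity to either test for HIV at the event or (depending on intervention arm) take home a HIVST kit". Two girls with the same attendance, knowledge and empowerment are still offered different services in the two arms. Part of the arm effect can therefore bypass the listed mediators even when they are modelled jointly.

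**3. Inputs for an illustration.** The plan states no power or sample size for mediation, so there is no figure of its own to reproduce. From section 8c: 60% versus 80% testing uptake, ICC 0.1, 100 girls per school, alpha 0.05, and 16 or 18 schools. As a check on these inputs, the design effect is 1 + 99 × 0.1 = 10.9. Nine schools per arm then give 900 / 10.9 = 82.6 effective girls per arm and 80.7% power, which agrees with the stated beta of 0.2. Eight per arm give 75.8%.

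**4. Normal approximation, half the effect mediated.** Assumed: SE(indirect) = SE(total) / 3, with independent direct and indirect estimates. At nine schools per arm:
- SE(total) = √[(0.24 + 0.16) / 82.6] = 0.0696
- SE(indirect) = 0.0696 / 3 = 0.0232
- SE(direct) = √(0.0696² − 0.0232²) = 0.0656

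The 10-point indirect effect is significant in 99.1% of draws and the equally large direct effect in 33.2%. The rule is met in 48.6%. In 32.9%, both effects are significant and no printed conclusion applies. With more schools the rule is met less often: 40.5% at 18 per arm, 13.8% at 36 and 0.9% at 72. Power for the indirect effect meanwhile goes to 100%.

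**5. Clustered simulation.** There were 10,000 trials per row, so the Monte Carlo standard error is at most 0.5 points. A latent normal model gives the binary outcome. The total effect is Φ⁻¹(0.80) − Φ⁻¹(0.60) = 0.588 SD and the latent ICC is 0.174 (binary ICC 0.10). Assumed: exposure is study arm, mediator ICC 0.1, mediator–outcome path 0.4 SD. The arm effect on the mediator is then share × 0.588 / 0.4, or 0.735 SD at a 50% share. The two-mediator rows use causally dependent mediators modelled jointly (each path to the outcome 0.3, first to second mediator 0.3). Linear models stand in for the planned method. Cells are 16 / 18 schools.

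| Scenario | Printed rule met | Direct-effect condition dropped | Loss (points) |
|---|---|---|---|
| One mediator, 25% | 15.6 / 15.8% | 45.4 / 51.4% | 30 / 36 |
| One mediator, 50% | 44.4 / 46.6% | 71.8 / 77.7% | 27 / 31 |
| One mediator, 75% | 61.8 / 66.4% | 72.4 / 78.2% | 11 / 12 |
| One mediator, 100% | 69.4 / 74.5% | 72.7 / 78.0% | 3 / 4 |
| Two jointly, 50% | 40.8 / 45.4% | 63.6 / 70.9% | 23 / 26 |
| Two jointly, 75% | 59.6 / 63.8% | 68.1 / 73.7% | 9 / 10 |
| Two jointly, 100% | 66.1 / 71.4% | 68.4 / 73.8% | 2 / 2 |
| Smaller effects (0.15 SD indirect, 0.15 SD direct) | 14.9 / 17.0% | 20.7 / 24.2% | 6 / 7 |

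A separate run of the one-mediator 50% row (3,000 trials) gave 43.6 / 46.2% against 71.2 / 78.2%. A separate run of the two-mediator 50% row gave 41 / 45% against 67 / 75%.

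**6. False positives without the condition.** With no arm effect on the mediators, a significant indirect and total effect occurred in 3.8 / 4.3% of trials (one mediator) and 2.6 / 2.8% (two jointly). When the arm moves the mediator but the mediator does not affect the outcome, it occurred in 3.7 / 4.1% (4,000 trials). Dropping the condition does not push the error above 5%.

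**7. Cluster unit.** The mediation text names only facilities. Sections 8a and 8c cluster and allocate by school, and the primary analysis in section 8f also clusters by school. Only SKILLZ-Plus is facility-based (section 4).

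**The case against.** The sentence does not say *only if* or *full mediation*, and indirect effects will be estimated and bootstrap-tested anyway. On that reading all that is missing is a label. It is true that the estimates will exist. But the plan attaches no conclusion to them, and the one rule it prints uses non-significance as supporting evidence.

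The exposure, called integration markers, is not defined. Both the expectation of a direct effect and the simulation take study arm as the exposure. This stands as a limit on the percentages. So does the fact that the causal diagram (Figure 1) is not available. Attendance at events offering services is itself a listed mediator, and if service access is modelled fully, the remaining direct effect and the loss could be small. The case table in step 1 needs neither assumption.

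The 27 / 31-point loss requires the arm to shift a single mediator by 0.735 SD. With a 0.3 SD shift (the smaller-effects row) the loss is 6 / 7 points. This is also correct, so the range should be quoted and not the headline alone.

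The total-effect condition, which the remedy keeps, is itself costly. With one mediator at a 50% share and 16 schools, the indirect effect alone is significant in 98.8% of trials, against 71.8% when a significant total effect is also required. That loss is as large as the one removed. Keeping the condition follows from question e, which concerns mediators of observed effects. The sponsor should accept that cost knowingly.

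Finally, SKILLZ-Plus comparators come from SmartCare records, for which no mediator measures are described. Naming the facility as the cluster does not supply them.

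**Conclusion.** The concern holds. The printed rule treats an undetected direct effect as support for mediation and gives no conclusion for a partial mediator with a detected direct effect. As precision improves, such a mediator becomes less likely to meet the rule. This follows from the wording alone and needs no simulation.

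The size is illustrative. Under the stated assumptions, dropping the direct-effect condition recovers 27 / 31 points for one mediator carrying half the effect and 23 / 26 points for two modelled jointly (16 / 18 schools). Across all scenarios shown, the range is about 2 to 36 points. It depends on the assumed exposure, mediated share and mediator effect, and on linear models. Only the Aim 2 process evaluation is affected; the primary outcome and sample size are not. The sentence should be changed, but the matter does not threaten the trial's main result.

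**What to change.** Replace the decision sentence in section 8f with wording such as:

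> Mediation will be concluded when the total effect is significant and the 95% confidence interval for the indirect effect excludes zero. The direct effect and the proportion mediated will be reported with 95% confidence intervals and are not criteria.

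Add two clarifications:
- Where mediators are causally dependent, report the joint indirect effect through the set, or state the extra assumptions needed for mediator-specific effects.
- State the cluster unit for the mediation analysis: school for SKILLZ-Girl and SKILLZ-Club, facility for SKILLZ-Plus.

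The cost is SAP wording only. The indirect effects and their bootstrap tests are already planned, and the surveys of enrolled girls in section 8d already collect the mediator measures. No new data are needed for the comparison between school arms, and naming the cluster for SKILLZ-Plus adds no data requirement of its own.
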